Safety Evaluations	The safety of the participants will be ensured by trained research staff and nurses from the UNC Clinical and Translational Research Center (CTRC), who will be on-hand for the intervention sessions, with the supervision of the PI. The co-investigating physician ([name]) will be on-call during all sessions, and the investigational drug service at UNC is available for consultation. A single dose of propranolol is expected to be very well-tolerated in this young, healthy population.
Statistical And Analytic Plan	To address our primary aim, we will conduct multilevel model (MLM) analyses examining levels of inflammation, with time (baseline, pre-stress, 30-, 60-, 90-min post-stress) as a within-subjects factor and condition (propranolol vs. placebo) as a between-subjects factor. We hypothesize that individuals in the placebo condition will show an increase in levels of the inflammatory marker IL-6 from pre- to post-stress, while those in the propranolol condition will show significantly lower levels of inflammation over time compared to the placebo condition (i.e., no stress-related increase in inflammatory markers). We will also conduct similar multilevel modelling analyses on our other secondary endpoints (i.e., cortisol, salivary alpha amylase, PEP, RSA, negative affect).
DATA AND SAFETY MONITORING PLAN	The PI and the project coordinator will be responsible for data quality management and ongoing assessment of safety. All data collected for the study will be stored on secure, password-protected servers maintained by the Department of Psychology and Neuroscience (or on secure, password-protected computers in the laboratory. Safety monitoring will be provided by the PI and the study physician, together with nurses from the UNC CTRC and the study coordinator.

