4.1 Intervention/Treatment procedures (by visits)

Session II (the intervention/treatment visit) will last approximately 5 hours and will take place in the emotion induction laboratory in Howell Hall at UNC-CH. When the participant arrives for the session, they will meet the lab manager and the nurse supplied by CTRC. The lab manager will give the participant a chance to review the consent form they signed during Session I, and will then remind the participant of the protocol and tasks in Session II. Once the participant understands the protocol and is comfortable with proceeding, the nurse will insert a catheter into the participant's non-dominant forearm, which will be used to draw all the blood samples. We use the catheter method so that participants do not have to be stuck with needles multiple times throughout the experiment. Once the catheter is placed, the participant will be given at least 45 minutes to acclimate to the catheter, during which time they will be prepared for psychophysiological data collection. We are collecting Heart Rate, Respiratory Sinus Arrhythmia, Cardiac Impedance, and Blood Pressure measures from participants throughout the session and, which will allow us to get a good index of participants' autonomic nervous system responses to the stress task, and will provide a biological "manipulation check" to ensure that the propranolol has had the intended effect (it should lower heart rate and blood pressure). Again, as with

Session 1, female research assistants will be assigned to female participants, while both male and female research assistants will be assigned to male participants, in an effort to reduce participant discomfort with the procedure of attaching the sensors. Once sensors have been attached, we will collect 5 minutes of baseline data while the participant just rests and relaxes.

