6.1 Primary Endpoint- Statistical Methods

Primary Objective 1. To examine if blocking sympathetic nervous system activity via the beta-blocker propranolol will attenuate inflammatory responses to stress.

Analysis Plan. To address this aim, we will first examine if there was a change in inflammation simply as an effect of taking the propranolol (before stress induction). As such, we will conduct a multilevel model (MLM) examining levels of inflammation (IL-6), with time (BL vs. pre-TSST) as a within-subjects factor and condition (propranolol vs. placebo) as a between-subjects factor. If the result of this test shows a significant interaction, then we will only include the pre-TSST time point in subsequent models. If non-significant, we will use both baseline time points in subsequent analyses. Next, we will conduct an MLM examining levels of inflammation, with time (BL and/or pre-TSST, 30-, 60-, 90-min post-TSST) as a within-subjects factor and condition (propranolol vs. placebo) as a between-subjects factor. We hypothesize that individuals in the placebo condition will show an increase in levels of inflammatory markers from pre- to post-TSST, while those in the propranolol condition will show significantly lower levels of inflammation over time compared to the placebo condition (i.e., no stress-related increase in inflammatory markers).

All outcomes will first be examined using histogram and scatterplot for assumptions of normality and homoscedasticity. Any variables that need to be log-transformed (e.g., cortisol, sAA, IL-6) will be before analyses are run. Across all models, we will evaluate if we need to control for sex, BMI, and objective SES.

Prior to analyses, we will also examine each outcome for outliers existing +/- 3 SDs from the mean within each time point within each condition. Outliers are excluded only within the time point where they were problematic but retained elsewhere to reduce data loss.

All data will be analyzed in R using the lme4 package. As time points are nested within individuals, we take a multilevel modelling approach with the inclusion of a random intercept to model individual differences in each outcome.

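### A preliminary significance test decides whether the pre-dose IL-6 sample enters the main model, the synopsis gives a different model, and no contrast is named as the test of attenuation

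*Combined protocol and SAP*

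**What the plan says.** Section 6.1 begins with a drug-only check: "we will first examine if there was a change in inflammation simply as an effect of taking the propranolol", using a model with time (BL, pre-TSST) and condition. The result sets the main model. One outcome removes BL: "If the result of this test shows a significant interaction, then we will only include the pre-TSST time point in subsequent models". The other outcome keeps it: "If non-significant, we will use both baseline time points in subsequent analyses". Section 6.2 applies the same procedure to every secondary outcome.

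The main IL-6 model is described by its factors, "with time (BL and/or pre-TSST, 30-, 60-, 90-min post-TSST) as a within-subjects factor" with condition between subjects, and by its random part: "we take a multilevel modelling approach with the inclusion of a random intercept to model individual differences in each outcome". No coefficient, contrast or reference time is named as the test of attenuation.

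The hypothesis has two halves. Placebo participants should rise from before to after the TSST, and "those in the propranolol condition will show significantly lower levels of inflammation over time compared to the placebo condition". A parenthesis then explains the second half as the absence of a stress-induced rise.

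The synopsis (Statistical And Analytic Plan) states the primary model "with time (baseline, pre-stress, 30-, 60-, 90-min post-stress) as a within-subjects factor", with no preliminary test.

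**The concern.** BL is taken before dosing and pre-TSST one hour after it. A drug effect on resting IL-6 would therefore separate the arms at every sample except BL. The plan regards this as possible, since it tests for it. When the test is significant, BL is dropped and a constant shift cannot enter the time-by-condition test. When it is not significant, BL stays in and the shift adds to that test.

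The reference for the stress response is also ambiguous. The hypothesis points to pre-TSST against post-TSST, but it also speaks of lower levels over time, and the plan counts BL and pre-TSST together as baseline. The comparison that answers the primary objective thus depends on a preliminary p-value, on whether section 6.1 or the synopsis is followed, and on which term of the model is read.

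**Working it through.** **Inputs from the documents.** 45 per arm (6.4) and two-sided 0.05 (6). Pre-TSST blood is drawn 60 min after dosing. The TSST lasts 2 + 10 + 5 = 17 min, so the later samples fall no earlier than 60 + 17 + 30 = 107, 137 and 167 min after dosing (4.1 Intervention/Treatment procedures). There is no power figure to reproduce: 6.4 bases the sample size on the arm sizes of earlier studies and gives no effect size or SD.

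**Assumptions.** SD 1 for log IL-6, no true attenuation, and a drug-only shift d that is constant from pre-TSST on. Covariance is either compound symmetry (CS) with correlation ρ = 0.5-0.9, or serial: half the variance between subjects and the rest with hourly autocorrelation 0.3-0.7.

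**Step 1: how a constant shift enters each test.** The arm differences at the five times are (0, d, d, d, d).
- Pre-TSST to mean post: d − d = 0.
- Omnibus on four times (BL dropped): no variation over time, so 0.
- Omnibus on five times: the mean is 0.8d, and the sum of squares is (0.8d)² + 4(0.2d)² = 0.80d².

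**Step 2: what the pretest detects.** The SE of the arm difference in change is √[2(1−ρ) × 2/45], which is 0.211 at ρ = 0.5 and 0.094 at ρ = 0.9. For d = 0.2 the ratios are 0.95 and 2.12, so power is about 15% and 55%; about 85% and 45% of such shifts are missed. For d = 0.5 the pretest detects 65% (ρ = 0.5) to 100% (ρ = 0.9). The shift detected with 80% power is 0.59 SD at ρ = 0.5 and 0.26 SD at ρ = 0.9.

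**Step 3: the synopsis omnibus test under CS.** The noncentrality is 0.80d² × 45/[2(1−ρ)]. For d = 0.2 this is 0.72/(1−ρ), or 1.44 at ρ = 0.5 and 7.2 at ρ = 0.9. With 4 and 352 degrees of freedom the test rejects in about 13% and 55%.

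**Step 4: the whole rule.** Simulation with 40,000 trials per setting and d = 0.2; entries are percentages of trials.

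| Covariance | Pretest significant | Section 6.1 rule, omnibus | Synopsis omnibus | Fixed contrast, pre-TSST to mean post |
|---|---|---|---|---|
| CS 0.5 | 15.3 | 7.2 | 13.0 | 4.8 |
| CS 0.7 | 22.6 | 9.5 | 19.8 | 5.0 |
| CS 0.8 | 31.4 | 11.3 | 28.2 | 5.2 |
| CS 0.9 | 55.4 | 14.9 | 55.0 | 5.2 |
| Serial 0.3 | 20.5 | 9.4 | 17.7 | 5.0 |
| Serial 0.5 | 26.4 | 10.0 | 21.8 | 5.0 |
| Serial 0.7 | 40.2 | 10.6 | 30.0 | 5.2 |

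The branch that keeps BL supplies 74-85% of the rule's omnibus rejections. For other shifts the rule's omnibus test rejects in 4-6% (no shift), 5-8% (0.1 SD), 10-15% (0.3 SD) and 5-15% (0.5 SD).

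**Step 5: a drug effect that keeps growing.** If the effect grows by a further 0.1 SD after pre-TSST, the fixed contrast itself rejects in 9-25% (CS) or 9-14% (serial).

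**The case against.** The strongest reply is that the hypothesis already fixes the comparison. It describes the placebo rise as before to after the TSST, glosses the between-arm half as no stress-related rise, and lists BL and pre-TSST as separate levels of time. On that reading the team would compare pre-TSST with post-TSST, and a constant shift cancels even with BL in the model. An omnibus rejection is also not yet a claim of attenuation. If it is claimed only when a significant pre-TSST to post-TSST contrast in the right direction supports it, the rate at 0.2 SD is 1-2.5%. Most of this stands. It shows that the wording is ambiguous rather than silent, and that the harm depends on how the result is read. It does not remove the gap, because nothing commits the team to that reading.

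A reader might also infer three stronger points that the documents do not support.
- **That the pretest is weak in general.** It is weak for small shifts only; at 0.5 SD it usually works. For the cardiac outcomes the plan expects a drug effect, since these measures are meant "to ensure that the propranolol has had the intended effect (it should lower heart rate and blood pressure"), and a large one would usually trigger the branch that drops BL.
- **That the two baselines are averaged.** A pooled-baseline contrast under the rule would reject in about 8-19% at 0.2 SD, but the plan enters the two samples as separate time levels and nowhere says that they are averaged.
- **That dropping BL isolates the stress effect.** It removes only a constant shift (step 5).

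**Conclusion.** The point holds in a conditional form and should be fixed before allocation is revealed. The plan has no rule that keeps a drug-only shift out of the attenuation claim, and its two descriptions of the primary model disagree. If the omnibus interaction is read as attenuation, a constant 0.2 SD shift raises rejection from about 5% to 7-15% under section 6.1 and to 13-55% under the synopsis.

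It would be wrong to infer that the primary test is inflated as it stands. The documents show no resting IL-6 effect; the SD, correlations and shift sizes are all assumed; with no shift there is no material inflation; and with a pre-TSST to post-TSST test a constant shift causes none.

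**What to change.** 1. Name the primary test as the between-arm difference in log IL-6 change from pre-TSST to the mean of the 30, 60 and 90-min samples, whatever the BL to pre-TSST result.
2. Together with (1), remove the pretest as a gate, align 6.1, 6.2 and the synopsis, and report the BL to pre-TSST arm difference with its CI as a separate drug-only estimate. Removing the gate alone would leave the five-time omnibus test, which does worse than the current rule.
3. Use the same contrast for secondary outcomes with a pre-TSST measure (cortisol, alpha amylase, PEP, RSA). For negative affect, state which pre-stress measure exists: section 4.1 clearly schedules only trait questionnaires before the TSST.
4. State the remaining limit. Section 1.3 puts the peak at 1-2 hours, pre-TSST blood is drawn at 1 hour, and there is no unstressed arm. A drug effect still growing after that sample cannot be separated from attenuation, with or without BL.

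**Optional safeguard.** Test the contrast on change scores. The 5% figures above are for change scores. Under serial correlation and no shift, the same contrast inside the random-intercept model rejects in about 7% with five times and 9-11% with four. Change scores lose any participant without a pre-TSST value, including one removed by the outlier rule, unless a missing-data rule is stated.

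**Cost.** SAP wording, with the same samples, plus the decision on negative affect. For a 0.3 SD attenuation and no pre-stress shift, power (named contrast / current rule's omnibus) is 41/37, 61/59, 78/78 and 97/98% for CS 0.5, 0.7, 0.8 and 0.9, and 45/45, 56/55 and 74/72% for serial 0.3, 0.5 and 0.7. That is no material loss. A loss of up to about 19 points arises only against the pooled-baseline contrast, which the plan does not state and which is valid only without a pre-stress drug effect.

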Upon completion of the baseline psychophysiological measures, participants will complete trait questionnaire measures while they continue to acclimate to the catheter and the laboratory environment. Once 45 minutes has passed (around 1:15 PM), the nurse will draw the first (baseline) blood sample, and participants will be asked to provide the first (baseline) saliva sample. Next, the oral tablet of propranolol or placebo will be administered to the participant by the nurse. Participants will continue completing trait questionnaires and once finished, they will be given neutral reading material (magazines) to read while drug activation takes place. One hour after administration of the medication (or placebo), the nurse will draw a second blood sample, and participants will be asked to provide a second saliva sample. We will also collect another 5 minutes of psychophysiological data.

Next, the Trier Social Stress Task (TSST; Kirschbaum, Pirke, & Hellhammer) procedures will be explained to participants. The TSST is a commonly-used acute stress test to measure psychological and biological responses to stress in the laboratory. In this task, participants will be asked to prepare for and give a 10-minute speech and complete a difficult mental arithmetic task as they are evaluated by trained interviewers. The nature of the task is stressful and participants may experience varying levels of stress, anxiety, and possibly embarrassment. The consent form at the beginning of the study describes that they will take part in a “role play” during a cognitive performance task (see Consent Form). We describe the task in this vague way in the initial consent because we want to ensure that the baseline physiology data is clean and not impacted by participants' anticipatory stress about the upcoming task. Additionally, prior to the participant's participation in the TSST, participants will be informed in greater detail about the procedure for TSST, and they will be asked if they would like to continue. If they do continue, but wish to stop at any time, they will be reminded that they can.

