6.2 Secondary Endpoints- Statistical Methods

Analysis Plan. To address secondary objectives, we will follow the identical procedure outlined above, but will swap in the relevant outcome as the dependent variable (i.e., cortisol, salivary alpha amylase, PEP, RSA, psychological responses). We will first examine if there was a change in the outcome simply as an effect of taking the propranolol (before stress induction). As such, we will conduct a multilevel model (MLM) examining levels of the outcome, with time (BL vs. pre-TSST) as a within-subjects factor and condition (propranolol vs. placebo) as a between-subjects factor. If the result of this test shows a significant interaction, then we will only include the pre-TSST time point in subsequent models. If non-significant, we will use both baseline time points in subsequent analyses. Next, we will conduct an MLM examining levels

of each relevant outcome, with time (BL and/or pre-TSST, post-TSST time-points) as a within-subjects factor and condition (propranolol vs. placebo) as a between-subjects factor.

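### When the pre-dose sample stays in the model, it gets a free mean in each randomised arm; one common baseline mean would add precision at no data cost, though not for the pre- to post-stressor change

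*Combined protocol and SAP*

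**What the plan says.** Section 6.1 analyses IL-6 in a multilevel model "with time (BL and/or pre-TSST, 30-, 60-, 90-min post-TSST) as a within-subjects factor and condition (propranolol vs. placebo) as a between-subjects factor", with a random intercept per participant. Section 6.2 repeats this for the secondary outcomes: "of each relevant outcome, with time (BL and/or pre-TSST, post-TSST time-points) as a within-subjects factor".

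A preliminary test of the condition-by-time interaction over BL and pre-TSST decides whether BL is used. One outcome of that test removes BL: "If the result of this test shows a significant interaction, then we will only include the pre-TSST time point in subsequent models". The other outcome retains BL alongside pre-TSST: "If non-significant, we will use both baseline time points in subsequent analyses".

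The order of sampling is in section 4.1 (Intervention/Treatment procedures). After catheter acclimation, "the nurse will draw the first (baseline) blood sample, and participants will be asked to provide the first (baseline) saliva sample". The tablet follows that sample: "Next, the oral tablet of propranolol or placebo will be administered to the participant by the nurse". And later: "One hour after administration of the medication (or placebo), the nurse will draw a second blood sample". BL is therefore pre-dose, and pre-TSST is post-dose.

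The only covariates considered in 6.1 are sex, BMI and objective SES. Section 3.2 has the drug service randomise with matching on age, gender and race. Baseline IL-6 appears in neither place.

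The hypothesis in 6.1 is worded in two ways: "individuals in the placebo condition will show an increase in levels of inflammatory markers from pre- to post-TSST", and lower levels over time on propranolol than on placebo. The final model's interaction term and the contrast that decides the primary objective are not written out.

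**The concern.** Random allocation makes the true arm means equal at a sample taken before dosing. A time-by-condition model that includes BL as an ordinary outcome level ignores this and estimates an arm difference that is known to be zero. Changes from BL then behave as change scores. A condition main effect averages in the chance BL difference, and comparisons of post-dose levels make no use of the BL value. The preliminary test is itself a BL-referenced change, so chance imbalance at BL also influences which model is fitted next.

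At stake is precision from samples already drawn, and protection against an unlucky imbalance in the trial as realised. Section 6.4 says that there are no grant funds to enrol more participants and that moderator analyses are intended, so precision matters here.

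**Working it through.** **The plan's own figure.** Section 6.4 gives 45 per condition, set from the average arm size in earlier studies and from practical limits. It states no effect size, SD, correlation or power, so there is no power figure to reproduce.

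**Inputs.** n = 45 per arm (6.4). Five IL-6 times: BL, pre-TSST, 30, 60 and 90 minutes (6.1). The random intercept implies equal correlation rho between all times (6.1). Values of rho are an assumption: 0.5 to 0.9. Outcomes are in SD units.

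**Size of chance imbalance.** The SE of the BL arm difference is √(2/45) = 0.21 SD, giving a 95% range of about ±1.96 × 0.21 = ±0.41 SD.

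**Method.** The vector of arm differences has covariance (2/n)Σ. For a contrast c, the free-BL variance is (2/n)c′Σc. With a common BL mean it is (2/n)[c′Σc − k²], where k is the covariance, under Σ, of the contrast with BL (BL variance 1). The proportion of variance saved is k²/(c′Σc), and k is also the regression of the contrast on the BL imbalance.

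| Contrast | c′Σc | k | Saving | rho 0.5 | rho 0.7 | rho 0.9 |
|---|---|---|---|---|---|---|
| One post-dose time − BL (includes the preliminary test) | 2(1−rho) | −(1−rho) | (1−rho)/2 | 25% | 15% | 5% |
| Mean of 30, 60, 90 − BL | (4/3)(1−rho) | −(1−rho) | 0.75(1−rho) | 37.5% | 22.5% | 7.5% |
| Mean of 30, 60, 90 − mean(BL, pre-TSST) | (5/6)(1−rho) | −(1−rho)/2 | 0.3(1−rho) | 15% | 9% | 3% |
| Mean of 30, 60, 90 − pre-TSST | (4/3)(1−rho) | 0 | 0 | 0% | 0% | 0% |
| Level at one post-dose time | 1 | rho | rho² | 25% | 49% | 81% |
| Condition main effect, five times | (1+4rho)/5 | (1+4rho)/5 | (1+4rho)/5 | 60% | 76% | 92% |

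The first row equals a variance ratio of (1+rho)/2. If power for that contrast were 80% under the planned model, a common BL mean would raise it to 90%, 86% and 82% at rho 0.5, 0.7 and 0.9.

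**Omnibus interaction (4 df).** This test is assumed, because the plan does not write it out. Take arm differences (0, 0, d, d, d):

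- free BL: noncentrality = (n/2) × 1.2 × d²/(1−rho)
- common BL: noncentrality = (n/2) × [d²/(1−rho)] × [3 − 9rho/(1+4rho)]
- ratio = [3 − 9rho/(1+4rho)]/1.2, which is 1.25, 1.18, 1.12, 1.07 and 1.03 at rho 0.5, 0.6, 0.7, 0.8 and 0.9

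For illustration only, with d = 0.3 SD, power goes from about 38% to 47% at rho 0.5, from 80% to 83% at rho 0.8, and from 98.7% to 99.0% at rho 0.9.

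**Saliva (four samples, two of them post-stressor).** The same calculation gives a ratio of 2 − 4rho/(1+3rho), which is 1.20 at rho 0.5 and 1.06 at rho 0.8.

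**The case against.** The strongest reply is that the hypothesis speaks of change from before to after the stressor. Under the plan's random-intercept covariance, BL has zero weight in post- minus pre-TSST, so imbalance at BL does not enter and the remedy gains nothing. This stands. A reader might infer that power is lost on the stress-response comparison itself; the documents do not support that. It does not dispose of the point, because 6.1 also hypothesises lower levels over time, names no deciding contrast, and runs a preliminary test that is BL-referenced.

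Second, the loss arises only where BL is kept. If the preliminary interaction is significant, BL leaves the model, and the remaining pre-stressor sample is post-dose, so randomisation would not justify constraining it. This also stands. The branch that drops BL is plausible for the cardiac outcomes, because section 4.1 expects the drug to lower heart rate and blood pressure. Where the drug has no pre-stressor effect, however, a valid 5% test keeps BL about 95% of the time.

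Third, the factorial mixed model is valid. A reader might infer that the planned estimate is biased; it is not, over randomisation. The issue is precision and balance in the realised trial.

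Fourth, the sizes rest on assumptions. All samples come from one session of about five hours, so a high rho cannot be excluded, and BL-referenced gains are then small. This stands as a limit on size. The gains for level comparisons and the main effect run the other way and grow with rho.

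**Conclusion.** The point holds as a free improvement, not as an error in the plan. When BL is retained, the model spends information on an arm difference known to be zero, and nothing else adjusts for baseline IL-6. The cost falls on the preliminary BL versus pre-TSST interaction, changes from BL, comparisons of post-dose levels, the condition main effect and any omnibus interaction. For BL-referenced changes it is moderate at rho near 0.5 and small at rho near 0.9; for post- minus pre-TSST it is zero.

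These sizes assume random allocation unrelated to IL-6, equal correlation between times as the random intercept implies, complete data, and, for the omnibus figures, equal effects at the three post-stressor times with none at pre-TSST. It is tempting to quote one figure as the trial's power loss, but the documents give no rho, effect size, final-model interaction or deciding contrast from which to derive it.

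**What to change.** In 6.1 and 6.2:

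1. Always keep BL. Remove the rule that drops it after a significant preliminary test.
2. Fit time at all levels including BL, with condition-by-time terms only for the post-dose times, so that BL has one mean across arms. Alternatively, enter the pre-dose value as a covariate and model only post-dose samples. The two agree under equal correlation and complete data, but a participant whose BL value is deleted under the outlier rule is lost from the covariate model and kept in the common-mean model.
3. Leave pre-TSST and all later times free by arm, because they are post-dose.
4. Apply this to every outcome with a pre-dose measurement.
5. Name the contrast that decides the primary objective, since the gain depends on it.

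The cost is a short rewrite of the model text in two sections, including removal of the switch. It needs no new samples or participants, and the model still runs in lme4.

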After being informed of the procedures and confirming participants would like to continue, the experimenter will introduce two more researchers who will act as the interviewers / judges. Participants will have 2 minutes to prepare for the speech, in which they will be asked to answer why they are the perfect candidate for their dream job. Participants will then give a 10 minute speech in front of the two interviewers and a video camera. After the 10 minute speech, participants will complete a verbal math task for 5 minutes. While participants are completing the tasks, interviewers will remain neutral (give neither positive nor negative feedback). The experimenter leading Session II will also be present throughout, to help with timing the tasks, etc.

Following completion of the TSST procedures, participants will complete a second round of questionnaires to measure their affective responses, somatic responses, and interpersonal appraisals during and after the TSST. Fifteen minutes after termination of the TSST, a third saliva sample will be taken, and 30 minutes after the termination of the TSST, a fourth (and final) saliva sample, and third blood sample, will be taken. Additional blood samples will be taken 60 minutes (sample #4) and 90 minutes (sample #5) following termination of the TSST. In between blood samplings, participants will be given neutral reading material. Following collection of the final blood sample, the nurse will remove the catheter and check the participant's vital signs. The nurse will then be dismissed back to the CTRC.

For the remaining 60 minutes of the session, participants will complete four computerized tasks designed to measure other psychological processes (besides stress) thought to be influenced by sympathetic nervous system activation. A list of tasks and questionnaires is included below.

In addition, at the completion of the study, participants will be fully debriefed. Contact information for the PI, Study Physician, and IRB is provided on the consent form and debriefing form (which participants can keep) if they wish to address any concerns they had.

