6. STATISTICAL CONSIDERATION

[name] and her trainees will be responsible for statistical computations and data analysis. She will consult with colleagues in the Quantitative Psychology area of the Department of Psychology and Neuroscience as needed. All hypothesis tests will be evaluated using 95% confidence intervals, corresponding to a *p* value or .05. Only tests that indicate a *p* value of .05 or less will be considered statistically significant; tests above this *p* value will not be interpreted.

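### The random-intercept-only model assumes equal correlation between all samples and no step checks it; if correlation decays with time, some IL-6 time contrasts miss their 5% level, though the omnibus interaction barely moves

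*Combined protocol and SAP*

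**What the plan says.** Section 6.1 analyses IL-6 with time as a within-subjects factor and condition as a between-subjects factor, in R with lme4. On the within-person structure it says only that "we take a multilevel modelling approach with the inclusion of a random intercept to model individual differences in each outcome". Section 6.2 applies the same procedure to the secondary outcomes.

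The number of times depends on a preliminary two-time test of baseline against pre-TSST: "If the result of this test shows a significant interaction, then we will only include the pre-TSST time point in subsequent models". Otherwise both are kept, so the default IL-6 model has five times and the alternative has four.

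The planned diagnostics are limited: "All outcomes will first be examined using histogram and scatterplot for assumptions of normality and homoscedasticity". Log-transformation and a 3-SD exclusion rule follow. Section 6 treats a p value of .05 or less as the criterion for interpreting any test. The hypothesis is that "individuals in the placebo condition will show an increase in levels of inflammatory markers from pre- to post-TSST", with lower levels over time on propranolol. No single contrast or interaction test is named as deciding.

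The sampling times come from the intervention procedures (Section 4.1): "One hour after administration of the medication (or placebo), the nurse will draw a second blood sample", and after the +30 min draw, "Additional blood samples will be taken 60 minutes (sample #4) and 90 minutes (sample #5) following termination of the TSST".

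**The concern.** A random intercept with independent residuals implies equal variance at every time and equal correlation between every pair of times. The homoscedasticity check and the log-transformation bear on the variances. Nothing bears on the correlations: the plan has no random slope, serial correlation, sphericity check, degrees-of-freedom correction, robust standard error or model comparison.

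Samples taken close together may be more alike than samples taken hours apart. If so, one average within-person variance is too small for long gaps and too large for short ones. The error rate behind a reported p value would then depend on which contrast was reported, and no planned step would reveal it.

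**Working it through.** **Inputs from the documents.** 45 per arm (Section 6.4); nominal .05 (Section 6). Times in minutes after dose: baseline 0 and pre-TSST 60. A 5-min recording and a 2 + 10 + 5 = 17-min TSST put the TSST end 22 min after the pre-TSST draw, so the later draws fall at 112, 142 and 172. The 22 min leaves no time for explaining the task or introducing the judges, so a 40-min gap (130, 160, 190) was also tried.

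**Assumed, because the documents give no correlations.** Unit variance, and covariance between times j and k = p + e·r^(|tj − tk|/60), with noise n added on the diagonal:
- Constant: p = .7, n = .3.
- A (decay, no noise): e = 1, r = .8. Correlation is .89 at 30 min and .53 at 172 min.
- B (decay plus noise): e = .85, r = .8, n = .15. Correlation is .76 and .45.
- C (weak decay): p = .7, e = .15, r = .7, n = .15. Correlation is .83 and .75.

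**Formulas (complete, balanced data).** The random-intercept model estimates one within-person variance, with expectation MSE = mean variance − mean covariance. For a time contrast c:
- variance used by the model = MSE·c′c·(2/45)
- true variance = c′Σc·(2/45)
- ratio of model SE to true SE: q = √(MSE·c′c / c′Σc)
- actual error ≈ 2[1 − Φ(1.967q)], where 1.967 is the t critical value on 88 × 4 = 352 df
- a contrast with 80% power under the correct SE has power of about 1 − Φ(1.96q − 2.80)

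**The plan's own figure.** Under constant correlation q = 1 for every contrast and the formula gives 4.9%. Simulation gave 4.9-5.3% for contrasts and about 5% for the omnibus test. The .05 level holds under the model's own assumption.

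**Worked case, structure A, five times, 22-min gap.** Mean covariance .739, so MSE = .261.
- Baseline to 90 min: true 2(1 − .527) = .945; model 2 × .261 = .523; q = .744; error 14.4%.
- Mean of three post minus mean of two pre: c′c = 3/9 + 2/4 = .833; true .476; model .218; q = .676; error 18.4%.
- Pre-TSST to 30 min: true .352; model .523; q = 1.219; error 1.7%; power 80% falls to 66%.

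**Five-time model, error in % at 22-min gap (40-min gap in brackets).** The omnibus rows come from 40,000 simulated null trials per cell; the contrast rows use the formula.

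| Test | Constant | A | B | C |
|---|---|---|---|---|
| Omnibus interaction | 5.1 (4.9) | 7.7 (8.0) | 6.3 (6.3) | 5.4 (5.2) |
| Omnibus, with the preliminary baseline test | 4.2 (4.2) | 6.6 (7.1) | 5.4 (5.6) | 4.6 (4.4) |
| Pre-TSST to 30 min | 4.9 (4.9) | 1.7 (2.8) | 2.8 (3.6) | 4.0 (4.4) |
| Pre-TSST to 60 min | 4.9 (4.9) | 5.0 (5.9) | 5.0 (5.5) | 5.0 (5.2) |
| Pre-TSST to 90 min | 4.9 (4.9) | 8.5 (8.9) | 7.0 (7.4) | 5.8 (6.0) |
| Baseline to 90 min | 4.9 (4.9) | 14.4 (13.9) | 10.6 (10.5) | 7.2 (7.2) |
| Mean post minus mean of both pre | 4.9 (4.9) | 18.4 (20.0) | 13.2 (14.7) | 8.4 (9.2) |

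Separate simulations at the 22-min gap (20,000 null trials per structure) agree within about 0.7 points. Over eleven decaying structures, some weaker than C, they range over 5.5-15.4% for baseline to 90 min and 5.9-18.9% for the averaged contrast. In A, B and C, 80% power for pre-TSST to 30 min becomes 66%, 73% and 78% (73%, 76% and 79% with the 40-min gap).

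**Four-time model, unconditional.** Pre-TSST to 30 min is 3.7 / 4.2 / 4.7% for A / B / C with the 22-min gap and 5.0-5.2% with the 40-min gap, so the power loss is small or absent. Pre-TSST to 90 min is 13.3 / 9.4 / 6.6%.

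**Saliva (0, 60, 97, 112 min).** Over the eleven structures, pre-TSST against mean post is 4.0-5.1%, so it is not inflated. Baseline to +30 min is 5.2-14.1%.

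**Unstructured covariance.** On the same complete data it gives 4.5-5.4% throughout. The plan also deletes outlying values: "Outliers are excluded only within the time point where they were problematic but retained elsewhere to reduce data loss". With that rule applied (about 0.7 values lost per trial), it gives 4.7-5.8%.

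**The case against.** The strongest reply is that the documents contain no evidence of decay. The natural reading of Section 6.1 is an omnibus condition-by-time test, and run with the plan's preliminary baseline test it stays at about 4-7%. That stands, and it limits the point.

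A reader might infer that the primary analysis carries almost four times its stated error. The documents do not support this. That figure is the upper end of an assumed range, for a contrast the plan never names, under structures with little or no assay noise. Under weak decay the same contrast is at about 8-9%.

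Two further generalisations also fail. The loss of power at 30 min belongs to the five-time model, and averaged contrasts are not inflated everywhere, as the saliva result shows.

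Nor do the four-time rates describe that branch as it would be run. Without a drug effect, it is reached only when the preliminary test is significant, in about 5% of trials. Given that, the four-time omnibus error is about 14-15% even under constant correlation, and about the same with an unstructured covariance. This is a separate selection effect that the present fix does not cure.

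What remains is that the plan does not commit to the omnibus test. Its hypothesis concerns a change from before to after stress, so contrasts are likely to be reported, and their error then depends on an unchecked assumption.

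**Conclusion.** The point holds in conditional form. The specified model assumes equal correlation between all samples, and nothing planned would detect a departure. Under constant correlation the unselected tests are at about 5%.

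If correlation decays as in the three worked structures, the five-time IL-6 model gives:
- about 7-15% for baseline to 90 min
- about 8-20% for mean post minus mean of both pre-stress samples
- about 6-9% for pre-TSST to 90 min
- about 2-4.5% for pre-TSST to 30 min, with some loss of power
- about 5-8% for the omnibus interaction

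Weaker decay brings all of these closer to 5%. The sizes rest on the assumed covariances and sampling gaps, 45 per arm and complete data. Larger amounts of missing data were not simulated. This is an inexpensive improvement to the analysis, and it does not show that the planned primary test is invalid.

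**What to change.** In Sections 6.1 and 6.2, for IL-6 and the other blood and saliva outcomes with a small fixed set of three to five times, fit categorical time, condition and their interaction. Use an unstructured within-person covariance (for example the R package mmrm) and Kenward-Roger or Satterthwaite degrees of freedom. Amend the sentence that assigns all analyses to lme4. For PEP and RSA, apply this only if the recordings are reduced to a few fixed epochs, because the number of epochs is not given and the method was not tested for many. The two-time baseline against pre-TSST test needs no change.

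The cost is SAP wording and a different R call, with 15 covariance parameters for five times (5 × 6/2) or 10 for four (4 × 5/2) in 90 people. If correlation is in fact constant, the power lost is small:
- 0.35 SD contrast at correlation .8: 74.5% to 73.8% (0.7 points)
- 0.5 SD contrast at .7: 86.3% to 85.7% (0.6 points)
- omnibus test with arm differences of 0, 0, 0.2, 0.35 and 0.35 SD at .7: 66.9% to 64.8% (2.1 points)

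The incomplete-data check used an 88-df scaling, so the behaviour of the recommended degrees-of-freedom methods in this trial was not itself simulated.
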